359 Hazard ratios of sexual dysfunction associated with treatment of interest (esomeprazole) versus
360 comparators will be estimated using a Cox proportional hazards model.

361

362 **4.7.4. Sensitivity analysis**

363 The following sensitivity analyses will be performed to test the validity of the underlying assumptions
364 and the robustness of the study findings:

365 **Applying "per-protocol" (PP) approach:** In this analysis, the follow-up of patients will be censored
366 at the initiation of a PPI or H2RA other than the baseline treatment. Assuming that such censoring is
367 independent of the risk of SD (i.e., non-informative censoring), this analysis will estimate the
368 treatment effect had patients remained on the baseline treatment for the entire follow-up or
369 discontinued the baseline treatment but without initiating an alternative PPI/H2RA.

370 Thus, we will consider a patient to respect the baseline treatment protocol from index-date to the date
371 of crossing over to an alternative treatment arm. Patients will be censored at the earliest of the
372 following events: end of index-treatment, crossing over to an alternative treatment arm, first outcome
373 event date, loss to follow-up (e.g., transfer out date from the general practice in IMRD or end of
374 continuous observation of the patient by the practice in IQVIA™ DA Germany, or date of last data
375 collection from the practice), date of death or at the end of the study period.

376 This approach addresses the situation in which a patient initiates another PPI/H2RA after index-date,
377 which might be problematic if the other PPI/H2RA initiated after index-date and within the 1-year
378 follow-up might cause the outcome event instead of the baseline treatment.

379 It should be noted that the difference between the ITT and PP approach will lie in the follow-up period.
380 The same baseline conditions such as eligibility criteria and washout period before index-date were
381 applied for both analytical approaches.

382 **Adjustment for informative censoring at treatment discontinuation in the PP analysis:** In the
383 per-protocol analysis described above, patients will be censored when they initiate another treatment.
384 Implicit in the per-protocol analysis is an assumption that censoring is independent of the studied
385 outcome, so that this differential treatment selection should not introduce bias.

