386 In this analysis, we will adjust for potential selection bias via informative censoring, by reweighting
387 patient observations using the inverse of the probability of being censored at the initiation of another
388 treatment conditional on the same confounders selected at baseline (i.e., outcome risk factors
389 potentially associated with treatment initiation) but updating their values during follow-up. (Hernan et
390 al., 2000; Robins et al., 2000)

391

392 Analyses will be done using SAS Enterprise Guide 7.1 software.

393

394 **4.7.5. Sample size**

395 The sample size will be driven by the availability of individuals with exposures and outcomes within
396 each database and no *a priori* sample size requirement will be stipulated.

397

398 **4.8. Quality control**

399 The study will be conducted according to the ENCePP code of conduct (European Medicines Agency
400 2018).

401 Standard operating procedures or internal process guidance will be adhered to for the conduct of the
402 study. These procedures include rules for secure and confidential data storage, quality-control
403 procedures for all aspects of the study from protocol development to the reporting of the results.

404 All documents will undergo at least one round a review by an experienced reviewer, while the results
405 from the statistical analysis will be either reviewed or checked via double coding.

406 The quality control of the data is the responsibility of the data holder.

407 **4.9. Limitations of the research methods**

408 Exposure misclassification may exist since neither OTC drug use nor medication use during
409 hospitalisation are captured in the included databases. This is a particular issue because of the availability
410 of OTC PPIs has increased over time (Johnson et al., 2017) and, probably their OTC use. Additionally,
411 information on the actual duration of treatment corresponding to each prescription is not available and
412 is difficult to estimate since patients may be prescribed large packs and instructed to use the drug as
413 needed, with possible discontinuation/restart and dose-variation over time. Moreover, whether patients
414 collected their prescriptions or consumed the prescribed medication is unknown. Due to this uncertainty
415 and considering information from individual case reports about the latency of effect, we chose to follow
416 patients for a maximum of one year and attribute the entire follow-up to the index treatment unless

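### Section 4.7.4 gives two incompatible per-protocol censoring rules: the itemised list censors at end of index treatment, but the stated target, the weights and section 4.9 imply censoring only when another PPI/H2RA is started

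*Protocol*

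**What the plan says.** All of the following is in Protocol section 4.7.4 unless another section is named.

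- **Opening sentence of the PP approach.** Follow-up is censored "at the initiation of a PPI or H2RA other than the baseline treatment. Assuming that such censoring is" independent of the risk of sexual dysfunction (SD).
- **Target effect.** The effect had patients stayed on the baseline treatment for the whole follow-up or "discontinued the baseline treatment but without initiating an alternative PPI/H2RA".
- **Adherence window.** "Thus, we will consider a patient to respect the baseline treatment protocol from index-date to the date" of crossing over to another arm.
- **Itemised censoring list.** The earliest of the "following events: end of index-treatment, crossing over to an alternative treatment arm, first outcome" event, and then the administrative endpoints.
- **Rationale.** The approach deals with a patient who starts another PPI/H2RA within the year, because that drug might be the cause of the event.
- **Weighted analysis.** Its heading is "Adjustment for informative censoring at treatment discontinuation in the PP analysis". Its text restates the rule: in the "per-protocol analysis described above, patients will be censored when they initiate another treatment". The weights reweight "patient observations using the inverse of the probability of being censored at the initiation of another" treatment.
- **Section 4.9.** "information on the actual duration of treatment corresponding to each prescription is not available" and is difficult to estimate. Partly for this reason, the whole follow-up of up to one year is attributed to the index treatment unless another treatment is started.

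**The concern.** The censoring list is the text that a programmer would code, and section 4.7.4 says that ITT and PP differ only in the follow-up period. The list therefore defines the PP analysis. A man who stops his PPI and starts nothing else stays under observation according to the target, but leaves according to the list. Both rules cannot be programmed in one analysis.

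The PP analysis and its weighted version are the only two sensitivity analyses in section 4.7.4. If the list is followed, both would be reported as the effect of remaining on the drug or stopping without an alternative, when they estimate an effect during treatment only. The weights would not address censoring at stopping, and the analyst would have to construct an end date for which the protocol gives no rule.

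**Working it through.** **Step 1. Set the statements side by side.**

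| Place | Censors at start of another PPI/H2RA | Censors at end of index treatment |
|---|---|---|
| 4.7.4 opening sentence | yes | no |
| 4.7.4 target effect | yes | no; follow-up after stopping is expressly included |
| 4.7.4 adherence window | yes | no |
| 4.7.4 itemised list | yes | **yes** |
| 4.7.4 rationale | yes | not mentioned |
| 4.7.4 weighted analysis, restated rule | yes | no |
| 4.7.4 weighted analysis, weights | yes | not modelled |
| 4.7.4 weighted analysis, heading | not mentioned | names discontinuation |
| 4.9 attribution of follow-up | yes | no |

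Only the list, and the wording of one heading, point to stopping.

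**Step 2. Can the extra item be carried out as written?** The protocol gives no definition of end of treatment, such as days supplied, a gap allowance or an assumed course. Section 4.9 says that duration per prescription is not available, is difficult to estimate, and is complicated by large packs and as-needed use. For non-initiators (section 4.6, Cohort 6) the event does not exist, so in that comparison the item would act on one arm only.

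**Step 3. How much follow-up would it remove?** The protocol states no figure for this, so there is nothing to reproduce. The inputs are the recommended PPI course of 4-8 weeks and the one-year maximum follow-up, both from section 4.5. The share of follow-up kept is course days / 365.

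- 4 weeks: 28/365 = 7.7%
- 8 weeks: 56/365 = 15.3%

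This assumes one course per man with no refill or gap allowance. Table 1, footnote 1, and section 4.9 describe treatment as likely chronic, so other assumptions (mine, not the protocol's) are needed to show the range:

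| Assumption for the PPI arms | Share of the year kept |
|---|---|
| One course, no gap allowance | 8-15% |
| One course plus 30 days: (28+30)/365 to (56+30)/365 | 16-24% |
| One course plus 60 days: 88/365 to 116/365 | 24-32% |
| One course plus 90 days: 118/365 to 146/365 | 32-40% |
| Half treated all year, half one course: 0.5 + 0.5 x 0.077 to 0.5 + 0.5 x 0.153 | 54-58% |
| All treated all year | 100% |

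Under switch-only censoring, a man who never starts another PPI/H2RA keeps up to 100% in every row.

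**Step 4. Which arm limits the contrasts?** H2RA courses are longer: 8-12 weeks, so 56/365 = 15.3% to 84/365 = 23.0%. Both target arms are PPIs, however. Once every man in the target arm is censored, later comparator events fall in risk sets with one arm only and add nothing to the hazard ratio. The PPI share of 8-15% is therefore the relevant lower end for each planned contrast.

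**Step 5. Precision at that lower end.** With a roughly constant event rate, usable events fall in proportion to follow-up, and the standard error of the log hazard ratio grows by 1/sqrt(share): 1/sqrt(0.153) = 2.6 to 1/sqrt(0.077) = 3.6. At 100% kept, the factor is 1.

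**Step 6. Compare with reported onset.** Section 2 reports onset from a few days to five months. Five months is 5/12 = 42% of the year, which is later than the end of any single recommended course.

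**The case against.** The best defence is that the rest of the text largely settles the intended rule. Switch-only censoring is stated or implied throughout section 4.7.4 and in section 4.9. Box 2 describes the weighted analysis as adjusting for censoring at violation of the treatment protocol, and the adherence sentence says that protocol is respected until crossover. On this view the list item and the heading are slips, and the weights match the real rule. That is probably the intention. It does not remove the conflict, because the slip sits in the operative list. A statistical analysis plan that is not shown might define an end date, but the protocol's target and weights would still disagree with its list.

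Some stronger readings are tempting, but the documents do not support them.

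- **That the analyses will rest on 8-23% of the follow-up.** This needs one course per man with no refills, which sits badly with treatment described as likely chronic. The 23% belongs to H2RAs and limits no planned contrast (step 4).
- **That end of treatment cannot be dated at all.** Section 4.9 says that duration is not available and is difficult to estimate. An imputed date is possible; none is specified.
- **That the two rules will give different hazard ratios.** They can. If the hazard ratio were 1.5 for five months and 1 afterwards, the year average would be about 1 + 0.5 x 5/12 = 1.21, against 1.5 during an early course. That gap is built into the assumed pattern. With a constant hazard ratio and stopping unrelated to SD, both rules estimate the same value.
- **That the 15 men who improved after stopping (section 2) show informative stopping.** Their improvement followed onset, whereas follow-up here ends at the first recorded event. Men may stop because of symptoms not yet recorded, but these cases do not show it.
- **That cutting initiators while non-initiators run on biases the hazard ratio.** The longer comparator follow-up does not do so by itself, for the reason in step 4.

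**Conclusion.** The point holds as an internal contradiction. Section 4.7.4 states a target that includes follow-up after discontinuation and a censoring list that excludes it. The list item has no dating rule, does not apply to non-initiators and is outside the weight model. Following the list would turn both PP sensitivity analyses into on-treatment analyses under a label that says otherwise, with any stopping-related censoring left unweighted.

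The size is conditional. In the target arms the share of the year kept runs from about 8-15% (one recommended PPI course, no gap allowance) to close to 100% (continuous treatment). The protocol does not say where in that range the cohorts would fall. Neither the direction nor the amount of any change in the hazard ratio can be derived from it. The main ITT analysis is not affected. The passages should be reconciled, and this should be done before results are seen, so that the choice of rule cannot depend on them.

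**What to change.** 1. Delete the end-of-treatment item from the PP censoring list, so that protocol-related censoring occurs only at the start of another PPI/H2RA. This agrees with the stated target, the weights and section 4.9.
2. Rename the weighted analysis so that it refers to informative censoring at initiation of another PPI/H2RA instead of at discontinuation.
3. If an on-treatment analysis is also wanted, list it separately with its own target effect, a definition of end of treatment with a range of assumed durations, a statement of how non-initiators are handled, and censoring weights that model stopping.

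Items 1 and 2 change protocol wording only. They need no new data, and the switch-only rule takes less programming than the list as written. Item 3 is optional and would add programming and assumptions.

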299 washout) esomeprazole versus patients who: a) initiated other proton pump inhibitors (PPIs, namely
300 omeprazole, pantoprazole/lansoprazole); b) initiated histamine type 2 receptor antagonists (H2RA))
301 and c) patients who did not initiate treatment with either PPIs or H2RA but had received a diagnostic
302 for a PPI or H2RA indication (i.e. non-initiators comparators). Outcome events will be attributed to the
303 baseline treatment protocol regardless of treatment change during follow-up. (i.e., **intention-to-treat
304 analysis (ITT)**).

305

306 4.7.2. Descriptive analysis

307 Descriptive analyses will be performed to describe the study cohorts at baseline in terms of
308 demographic characteristics, lifestyle factors, potential indications, comorbidities, and history of
309 treatment with drugs commonly associated with sexual dysfunction.

310

311 4.7.3. Main statistical analysis

312 **Inverse probability of treatment weighting (IPTW)**

313 Inverse probability of treatment weighting (IPTW) will be used to render the assignment of study
314 treatments independent of the baseline measured covariates, thus minimising the potential
315 confounding effect of these covariates.

316 Using IPTW, the average treatment effect (ATE) in the entire study population will be estimated,
317 assuming that all important confounding variables have been accounted for. For each observation in
318 the study population, the IPTW is the inverse of the probability of receiving the observed treatment

319 conditional on all variables considered sufficient for confounding adjustment. In order to stabilize the
320 weights (i.e., less extreme weights, that are closer to the mean weight of one), the numerator of one
321 will be replaced by the marginal probability of receiving the observed treatment in the study population
322 (i.e., the proportion of observations in the study population with the respective treatment). (Hernan &
323 Robins, 2006) All analyses will then be conducted in the re-weighted population without additional
324 confounding adjustment on the assumption of no unmeasured confounding. To account for weighting
325 the population (essentially multiplying observations by the weight coefficient) robust standard error
326 estimators will be used (Hernan & Robins, 2020).

327 The distributions of baseline covariates before and after weighting was compared between

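### The informative-censoring weight in Section 4.7.4 inverts the probability of being censored; it should invert the probability of remaining uncensored

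*Protocol*

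**What the plan says.** Protocol Section 4.7.4 sets up a per-protocol analysis in which follow-up is censored "at the initiation of a PPI or H2RA other than the baseline treatment. Assuming that such censoring is" independent of the risk of sexual dysfunction. A second sensitivity analysis relaxes that assumption. It is headed "Adjustment for informative censoring at treatment discontinuation in the PP analysis". Its purpose is given as "In this analysis, we will adjust for potential selection bias via informative censoring, by reweighting", and the weight itself is defined by "patient observations using the inverse of the probability of being censored at the initiation of another" treatment. The probability is conditional on the baseline confounders, "potentially associated with treatment initiation) but updating their values during follow-up. (Hernan et".

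No other part of the protocol defines the censoring weight or refers to the probability of remaining uncensored. For the treatment weights, Section 4.7.3 states that for each observation in "the study population, the IPTW is the inverse of the probability of receiving the observed treatment". It adds that outcome analyses in the weighted population use no further adjustment for confounders.

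**The concern.** An inverse-probability-of-censoring weight lets each man still under observation stand in for similar men who have been censored. That requires the inverse of his probability of still being under observation. The printed weight uses the complementary probability, so men with the profile of those lost to switching get small weights and men who hardly ever switch get very large ones.

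This is the only planned analysis that relaxes the independent-censoring assumption of the per-protocol result. If it were programmed as written, a large shift after adjustment could be taken as evidence that switching was strongly informative, or as evidence for or against the safety signal, when the shift came from the weight.

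**Working it through.** The plan states no figure to reproduce. The check is algebra followed by illustrations on assumed inputs.

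**Algebra.** Let p(L) be the covariate distribution at baseline in one arm and c(L) the probability of being censored.
- Men still followed: proportional to p(L)·(1 − c(L)).
- Weight 1/(1 − c(L)): gives p(L), the full arm restored.
- Printed weight 1/c(L): gives p(L)·(1 − c(L))/c(L), the existing distortion multiplied by a further 1/c(L) in the same direction.

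The rule in Section 4.7.3 is the inverse probability of the status actually observed. For a man still in follow-up that status is uncensored, so the protocol's own principle leads to 1/(1 − c(L)).

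**Hand calculation (all inputs assumed).** 30% of men are high-risk; outcome risk is 4% (high) and 1% (low) in both arms, so the true ratio is 1.00. Switching (low/high risk) is 5%/30% in arm A and 5%/10% in arm B.
- True risk in each arm: 0.7×1% + 0.3×4% = 1.90%.
- Unweighted A: (0.665×1% + 0.21×4%)/0.875 = 1.72%. Unweighted B: (0.665×1% + 0.27×4%)/0.935 = 1.87%. Ratio 0.922.
- Printed weight A (1/0.05 = 20 and 1/0.30 = 3.33): (13.3×1% + 0.7×4%)/14.0 = 1.15%. Printed weight B (20 and 10): (13.3×1% + 2.7×4%)/16.0 = 1.51%. Ratio 0.763.
- Correct weight: 0.665/0.95 = 0.7 and 0.21/0.70 = 0.3 in A, and 0.27/0.90 = 0.3 in B, so 1.90% in both arms. Ratio 1.000.

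**Person-time version (all inputs assumed).** 50% of men are high-risk, sexual dysfunction rates are 2 and 6 per 100 person-years, the true ratio is 1.00, and there are 12 monthly intervals with censoring applied at the start of each. The range for the printed weight covers two readings: the probability of censoring in the month, or by that month.

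| One-year switching, low/high risk (arm A vs arm B) | Unweighted | Printed weight | Correct weight |
|---|---|---|---|
| 10%/40% vs 10%/10% | 0.95 | 0.65–0.66 | 1.00 |
| 10%/30% vs 10%/15% | 0.975 | 0.80–0.81 | 1.00 |
| 10%/12% vs 10%/10% | 0.997 | 0.95 | 1.00 |
| 10%/30% vs 10%/30% | 1.00 | 1.00 | 1.00 |

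Censoring at the end of each month instead changes the first row to 0.96, 0.65–0.67 and 1.00.

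**How general is it?** In 100,000 random two-stratum scenarios (high-risk share 5–95%, censoring 1–60%, outcome risk 0.2–8%, true ratio 1.00), the printed weight made the within-arm bias worse in all of them and the between-arm bias worse in 94%.

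**Stabilisation.** In the first row of the table, a numerator conditional on baseline covariates makes every weight equal to 1, because the risk factor is a baseline one. The ratio stays at 0.948, the same as with no weighting. A numerator conditional on arm and time only gives 1.00.

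**The case against.** The strongest reply is that this is loose wording for standard censoring weights. The stated aim is right, the treatment weights follow the right principle, and monthly weights of about 24 to 114 (1/0.0417 and 1/0.0087 in the 10%/40% arm) would draw attention. Section 4.8 also provides for review or double coding. All of that lowers the chance that the error reaches the results. It does not correct the text, which states the estimator explicitly, and two programmers working from the same sentence could agree on the same wrong weight.

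A second reply concerns size. The 0.65 needs a common risk factor and strongly risk-dependent switching in one arm only, and the document supplies none of these inputs. That stands: the figures show direction and a possible range, and are not a forecast.

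A reader might infer that the printed weight always pushes the hazard ratio further from the truth. The documents do not support that. With identical switching in both arms the ratio is unaffected, although each arm's rate is still distorted, and about 6% of the random scenarios showed no worsening between arms. Even the within-arm result was shown only for a single binary risk factor; it extends to cases where risk moves in one direction with the probability of censoring.

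A reader might also infer that the study's main finding is at risk. It is not: the intention-to-treat analysis does not censor at switching.

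**Conclusion.** The weight is wrong as written and should be corrected before the analysis is run. The inversion follows from the text and the algebra alone. In general it increases the selection bias within an arm, and it usually takes the hazard ratio further from the truth when switching depends on risk differently in the two arms. The size depends on switching rates that the documents do not give: with a true ratio of 1.00, the differential-switching rows of the person-time table run from 0.95 down to 0.65 under the printed weight, against 0.997 down to 0.95 unweighted.

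The consequence is limited to one sensitivity analysis. The main analysis and the unweighted per-protocol analysis stand as they are. This is a correction that should be made, not a flaw that invalidates the plan. Whether the program code repeats the error cannot be told from the protocol.

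**What to change.** Replace the definition of the weight in Section 4.7.4 with: *reweighting person-time by the inverse of the cumulative probability of remaining uncensored up to each time, conditional on treatment arm and on baseline and time-updated confounders, multiplied by the treatment weight.*

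If the weights are stabilised, make the numerator conditional on treatment arm and time only. A numerator that includes baseline covariates would leave selection on those covariates in place, and Section 4.7.3 allows no covariate adjustment in the outcome model to deal with it.

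Separately, reconcile the event being modelled. The heading of this analysis refers to discontinuation and the text beneath it to starting another treatment. The per-protocol paragraphs list the end of the index treatment as a censoring event, yet also describe men who stop without starting an alternative as still followed. The censoring model should cover whichever event or events are kept.

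The cost is one sentence for the weight and a consistent statement of the censoring event. No new data are needed.

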174 ¹ These indications are selected indications for PPIs and H2RAs. We restricted the study population to patients with
175 chronic indications, for which treatment is likely chronic. The rationale for this is explained in Limitations (first
176 paragraph)

177 ² These are assumed to be proxies of indications (e.g., PPIs are indicated to patients requiring continued NSAID or
178 antithrombotic therapy).

179

180 **4.4. Recruitment period**

181 The recruitment period will start on January 1st, 2005, and will end on December 31st 2020 in both
182 IQVIA™ DA Germany and IMRD UK.

183 Although the first use of esomeprazole dates to September 2000, in IMRD UK and October 2000, in
184 IQVIA™ DA Germany, we opted to include data from 2005 the year when the distribution of male
185 sexual dysfunction events started being consistent.

186 Additionally, we opted to limit the recruitment period up to 2020 because the use of H2RAs is very
187 limited in IQVIA™ DA Germany after 2020. Of note, the suspension of all ranitidine medicines in the
188 European Union due to the presence of low levels of an impurity called N-nitrosodimethylamine
189 (NDMA) in April, 2020^[1] led to the suspension of ranitidine, the dominant H2RA in Europe.

[figure not shown]
190

191 **4.5. Follow-up period**

192 Patients will be followed-up from index-date up to maximum one year. For instance, patients recruited
193 in 2020 can be followed up to 2021. Thus, patients will be followed-up from index-date to the earliest
194 of: date of first occurrence of outcome, loss to follow-up (e.g., transfer out date from the general
195 practice in IMRD or end of continuous observation of the patient by the practice in IQVIA™ DA
196 Germany, or date of last data collection from the practice), death (only available in IMRD UK), end of
197 follow-up (1 year) or end of the study period.

198 Considering the recommended duration for these treatments (4-8 weeks for PPIs and 8-12 weeks for
199 H2RAs), a patient may participate with several treatment episodes - and consequently index-dates -
200 during the study period. For example, a patient may receive a prescription for 8 weeks after which the
201 medication is discontinued to assess the need for ongoing therapy (on-demand or intermittent use).
202 After 15 months of discontinuing this therapy, the patient may receive another prescription for the
203 same therapy and duration. Therefore, this patient will enter the study twice and contribute with two

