417 another treatment was initiated. It should be noted that, in the analysis comparing with non-initiators,
418 we restricted the study population to patients with chronic indications, for which treatment is likely
419 chronic.

420 To our knowledge, the accuracy of diagnostic coding for sexual dysfunction has not been assessed in the
421 primary care databases available. However, the nature of the diagnosis means that its recording in
422 primary care records could be reasonably accurate, particularly for sexual dysfunction in male individuals.
423 Nonetheless, this assumption should be treated cautiously. In the UK, the patent for Viagra expired in
424 June 2013, which followed a drop by 93% in the price of generic preparations of sildenafil compared to
425 the price of branded Viagra (Connelly, 2017). Besides, Sildenafil has been available OTC without
426 prescription from UK pharmacies since 2017 and, therefore, patients have no longer needed to see their
427 doctor to get a diagnosis ever since. (MHRA, 2017) These events led to marked changes in diagnosis
428 coding practices of erectile dysfunction during 2013-2014 and marked decrease of coding for impotence
429 by GPs since 2017 which are reflected in the distribution of outcome events over calendar time. In
430 IQVIA™ DA Germany the reporting of male sexual dysfunction appears stable after 2005. To account for
431 uncertainties around potential misclassification due to changes in diagnostic criteria or coding practices
432 over time, calendar period will be adjusted for in the analysis.

433 It also needs to be considered that patient's medical history, as captured by GP practices included in
434 the study, may be incomplete, particularly in the IQVIA DA Germany database. In Germany, there is
435 no mandatory GP system and patients have free doctor choice. A specialist can be consulted without
436 referral from the GP. As a result, data are collected from visits to various medical practices which are
437 not linked by a unique patient identifier. Therefore, the entire medical history of patients might be
438 fragmented and for that reason there is a risk of exposure, outcome and covariates misclassification.
439 However, this misclassification will affect both target and comparator groups.

440 Although confounding by indication represents a common source of bias, it is not likely that the main

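### UK outcome recording is not consistent over 2005-2020 as section 4.4 implies, and the calendar adjustment in section 4.9 protects the UK hazard ratio only in part and UK incidence not at all

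*Protocol*

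**What the plan says.** Section 4.4 sets one window for the two databases: "The recruitment period will start on January 1st, 2005, and will end on December 31st 2020 in both" of them. The reason for the start is outcome recording: "we opted to include data from 2005 the year when the distribution of male" "sexual dysfunction events started being consistent". Neither database is exempted. The end date has a different reason: "Additionally, we opted to limit the recruitment period up to 2020 because the use of H2RAs is very" limited in the German database after that year.

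Section 4.9 separates the two countries. German reporting is described as stable after 2005. For the UK, sildenafil became available without "prescription from UK pharmacies since 2017 and, therefore, patients have no longer needed to see their" doctor for a diagnosis. The section reports marked shifts in "coding practices of erectile dysfunction during 2013-2014 and marked decrease of coding for impotence" "by GPs since 2017 which are reflected in the distribution of outcome events over calendar time". No size is given for either shift, and no direction for the 2013-2014 change.

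The stated response to possible misclassification is that "over time, calendar period will be adjusted for in the analysis". Section 4.6 lists calendar year as a baseline covariate, and section 4.7.3 places all adjustment in the treatment weights. Non-initiators are also matched on index date. The two sensitivity analyses in section 4.7.4 concern treatment switching; neither addresses outcome recording.

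**The concern.** Section 4.6 says the endpoint is driven mostly by erectile dysfunction and impotence, so the UK shifts affect its main component. Section 4.4 treats recording as settled from 2005 in both countries, and section 4.9 contradicts that for one of them.

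Section 4.9 then presents calendar adjustment as the answer to misclassification. Weighting on year of entry makes arms comparable in when they entered. It cannot bring back events that were never coded. This matters in three places:

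- **Absolute risk.** Section 4.7.3 reports incidence rates and cumulative incidence by arm, and section 4.9 gives background risk as a purpose of the non-initiator arm. UK figures from 2017 will be too low however the arms are weighted.
- **Recording that differs by arm.** If capture now depends more on GP contact, it could differ between men prescribed a drug at index and men who were not. The section 4.6 covariates include no measure of consultation frequency.
- **Eligibility.** The exclusion for prior SD or SD treatment uses the same records, so after 2017 men who treated SD over the counter can enter as event-free.

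**Working it through.** The protocol gives no event counts, sample size or size of the recording shifts, so there is no planned figure to reproduce. The check below is an expected-value calculation on one-year risks; at the low risk assumed, risk and hazard ratios nearly coincide.

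**From the protocol.** There are 16 index years, 2005-2020. Index years 2013-2020 are 8/16 = 50% and 2017-2020 are 4/16 = 25%. Entrants in 2016 also have follow-up reaching into 2017. Shares of patients or events by year cannot be computed.

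**Assumed.** True one-year comparator risk is 1.5%. Recording relative to 2005-2012 is 1.2 to 1.5 in 2013-2016 and 0.3 to 0.8 in 2017-2020. The target arm is spread evenly over years. The comparator is either even or falls linearly to 50% or 20% of its 2005 level (Box 1 says H2RA prescribing declined).

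**1. Recording shifts equally in both arms.** Let r(y) be relative recording in year y and RR the true ratio. After weighting on year, both arms have the same year distribution w(y), so

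observed ratio = RR × Σ w(y)r(y) / Σ w(y)r(y) = RR.

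The calculation returns 1.000 for a true 1.00 and 1.300 for a true 1.30 in every scenario. Without weighting, a declining comparator gives 0.93-0.99 and 1.21-1.29. Calendar adjustment is therefore needed, and it works under this condition.

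The result also needs near-perfect specificity. With an assumed 0.1% false positives and a true ratio of 1.30, the observed ratio is 1.28 at full recording. At 30% recording it is

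(0.3×0.0195 + 0.001×0.9805) / (0.3×0.015 + 0.001×0.985) = 1.25.

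**2. Target arm recorded more often from 2017, by a factor d.** Observed ratio = RR × Σ w(y)r(y)d(y) / Σ w(y)r(y), with d(y) = 1 before 2017. With even arms, RR = 1.00 and recording 1.2 then 0.8:

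- d = 1.10: (8 + 4×1.2 + 4×0.8×1.10) / (8 + 4×1.2 + 4×0.8) = 16.32/16.00 = 1.020
- d = 1.25: (8 + 4.8 + 4×0.8×1.25) / 16.00 = 16.80/16.00 = 1.050

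| Target arm recorded more from 2017 | True 1.00, all scenarios | True 1.30, all scenarios |
|---|---|---|
| 10% | 1.006-1.020 | 1.307-1.326 |
| 25% | 1.014-1.050 | 1.318-1.365 |

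Calendar weighting does not remove this bias.

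**3. Absolute risk from 2017.** Recorded risk = relative recording × true risk. For a true 1.5%, recording of 0.8, 0.5 and 0.3 gives 1.20%, 0.75% and 0.45%. Weighting leaves these unchanged.

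Pooling can also hide the problem. With recording of 1.2 and then 0.8, the whole-period figure is (8 + 4.8 + 3.2)/16 = 1.00 of the 2005-2012 level, although two of the three periods are off. With 1.2 and then 0.5 it is 14.8/16 = 0.93.

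**The case against.** The protocol discloses the UK shifts, explains them, urges caution about coding accuracy and states a remedy. That remedy does what is needed for the hazard ratio when recording changes alike in all arms, and index-date matching reinforces it for non-initiators. Period-specific reporting is often left to an analysis plan, which section 7 mentions and which is not available here, so its absence from the protocol is not in itself a fault. All of this stands. The point rests on the conflict between sections 4.4 and 4.9, and on section 4.9 offering calendar adjustment for misclassification without stating its limits.

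It is also fair to say that no protocol text documents a difference in GP contact between arms; all arms need an indication or qualifying comedication and a year of recorded history. Any such difference would cause detection bias in every year, so a cut at 2016 would not remove it. Period-specific results could show only whether the contrast changes when recording does.

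A reader might infer more than the document supports:

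- **That recruiting up to 2020 rests on consistent recording.** Only the 2005 start does; the end date rests on H2RA use.
- **That UK recording collapsed.** The text reports a marked decrease without a size.
- **That the UK hazard ratio could be off by a quarter.** Capture of 50% against 40% would give 0.50/0.40 = 1.25, but only within affected years. Applied to index years 2016-2020, with even entry and full capture before, the pooled ratio is (11 + 5×0.50)/(11 + 5×0.40) = 13.5/13.0 = 1.04.
- **That UK incidence is understated throughout.** This is supported only from 2017, because the direction of the 2013-2014 change is not given.

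**Conclusion.** The point holds for IMRD UK only. The consistency statement in section 4.4 conflicts with section 4.9 for that database. Calendar-year weighting is a sound remedy for the hazard ratio under two conditions, equal shifts across arms within a year and near-perfect specificity, and the protocol states neither.

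The effect on the pooled hazard ratio is probably modest: from 1.00 to about 1.01-1.05 if the target arm is recorded 10-25% more often from 2017, under the assumed recording levels and arm distributions. The effect on absolute measures is more certain in direction. UK incidence, cumulative incidence and non-initiator background risk from 2017 will be under-recorded relative to earlier years, by an amount the document does not allow one to estimate. This should be corrected, but it does not undermine the main design, and nothing in section 4.9 suggests a comparable shift over time in the German data.

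**What to change.** For IMRD UK, in the protocol or the analysis plan, before results are seen:

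1. Keep the full-period analysis and add a sensitivity analysis with follow-up cut at 31/12/2016. This window still contains the 2013-2014 change, so it does not replace item 2.
2. Report incidence and hazard ratios by calendar period (2005-2012, 2013-2016, 2017 onward), with person-time split or censored at the boundaries so that, for example, 2012 entrants do not carry 2013 follow-up into the first period.
3. Base UK background risk on the period-specific figures, flag 2013-2014, and label figures from 2017 as under-recorded. Note there that the prior-SD exclusion is weaker from 2017.
4. In section 4.4, limit the consistency statement to Germany.
5. In section 4.9, say that calendar adjustment handles recording shifts common to all arms in the hazard ratio, but not absolute incidence or recording that differs by arm. Use one term, since section 4.6 refers to calendar year and section 4.9 to calendar period.

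The cost is some rewording and re-runs on existing data. The downside is wider intervals in the UK subsets.
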